8. RESEARCH QUESTION AND OBJECTIVES

The objective of this post-marketing observational study is to assess the impact on invasive meningococcal disease (all capsular groups) and effectiveness of 4CMenB vaccination against MenB and vaccine-type disease, after introduction of 4CMenB in the UK.

9. **RESEARCH METHODS**

The study is a post-marketing observational effectiveness study of 4CMenB vaccination, given as part of routine clinical care in England. Study throughout this protocol refers to the provision of customised post-marketing surveillance reports of independently generated data to assist GSK Vaccines in meeting its regulatory commitment.

Part of the study will be a prospective description of all reported meningococcal cases (all capsular groups) as reported through routine national surveillance to Public Health England (PHE) and its Meningococcal Reference Unit (MRU). Observations will start with introduction of the vaccine into routine clinical care in England and last for the 3-year study duration. Additionally, there will be retrospective reporting of the prospective collection of cases for the 3-year study duration.

The second part of the study will be analytical in nature and assess the effectiveness of the 4CMenB vaccine. The study duration will depend on the number of meningococcal cases required to reach sufficient precision, currently estimated to be 3 years. The screening method is proposed, unless issues with obtaining relevant coverage data call for alternative designs (e.g. the case-control method).

A figure with study timelines is included below (Figure 4).

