6. MILESTONES

Important milestones, such as start, duration and reporting of this study, largely depend on whether or not 4CMenB will be registered and introduced into the UK, under which circumstances (NIP or outbreak setting), and which age groups are indicated to receive the vaccine. A large NIP catch-up campaign would reduce the absolute number of reported meningococcal cases and as a result it will take more time before the required sample size has been reached. This would cause an increase of the total study duration and, therefore, a later date for the report(s) and publication(s).

We assume the total study (descriptive and analytical) will take 3 years, with another six months for the final report(s) and publication(s).

A figure of the estimated timelines was included earlier in this protocol (Figure 4).

Overview of study milestones.

Milestone	Planned date
Start of data collection	With launch in the UK NIP, expected 1 Sep 2015
End of data collection	3 years after study start
Study progress reports	Every 6 months for the 3-year study duration
Registration in the EU PAS register ENCePP	At least 4 week before study start
Submission to Ethics Committee/Institutional Review Board	NA, see section 10 (role of NIGB in approving national surveillance activities)
Final report of study results	6 months after end of the 3-year study duration

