9.7.1 Statistical Hypotheses

No hypothesis is tested. This study determines the impact on meningococcal disease and effectiveness of 4CMenB vaccination against MenB disease, after introduction of 4CMenB in the UK.

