9.7.3 Statistical Methods

For each of the proposed study designs, the statistical methods are as follows:

1. Descriptive (no hypothesis testing):

This study will provide a summary of the epidemiology of all capsular groups of meningococcal disease, e.g. by vaccination status, age, setting and method. The method will be purely descriptive and summarise the observed number of *N. meningitidis* cases reported to PHE, stratified by variable of interest. More details are described above.

2. Analytical study:

Vaccine effectiveness (VE) is generally defined as the % reduction in the attack rate in vaccinated compared with unvaccinated children in the same birth cohorts. VE will be assessed by the screening method, or by a case-control method if the screening method cannot be used (for example, if appropriate coverage data cannot be determined).

a. Screening method:

For this method, the VE can be estimated using the formula below, where PCV is the proportion of cases that are vaccinated and PPV is the proportion population vaccinated (coverage):

$$VE = 1 - (\underline{PCV \times (1-PPV)})$$
$$((1-PCV) \times PPV)$$

The vaccine effectiveness estimate will be calculated along with the 95% confidence interval using the exact binomial distribution for the proportion of cases vaccinated in each of the study settings.

b. Case-control method:

In case-control studies, vaccine effectiveness is based on the odds ratio (OR) and is defined as: VE = 1 - OR

The vaccine effectiveness estimate will be calculated along with the 95% confidence interval using the standard errors from logistic regression.

If it is decided to pursue a case-control method, for instance if uptake information is difficult to obtain, the three controls for each case would as a minimum be matched on age (same month of birth if that is sufficient to define vaccine eligibility for infants) and sex.

As mentioned earlier, additional calculations can be considered to investigate the doseresponse relationships for each antigen in the vaccine (versus having at least one antigen, as described in the secondary objective).

As the number of cases due to other capsular groups is expected to be too small for analysis within the study period, at a later stage, outside the scope of this study protocol, it could be envisioned to evaluate both cross protection against other capsular groups and any capsule replacement after introduction of the vaccine.

Subgroup analyses

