9.9 Limitations of the Research Methods

Reporting of meningococcal cases is based on passive surveillance which may be an underestimate of true disease. Additionally, the national surveillance system may not capture data from meningococcal patients that died from the disease. However, as meningococcal disease is a serious illness, we expect that not many cases will be missed and that even from deaths samples will be available for diagnostic confirmation of IMD. The main benefit of using national surveillance data is that the results may be generalisable to the whole UK population and potentially even beyond its borders.

GSK Vaccines S.r.l.		Observational Study Protocol V72_38OB
03 SEP 15 Version 3 Final	Confidential	Page 44 of 61

For the screening method, aggregated data will be used. The 'cost' of the simplicity is that no control for confounding is possible. However, in a NIP this should not be an issue. Also, the screening method provides a quick and proven design to perform this study.

The study may run into feasibility issues due to lack of precision of estimates, especially with high coverage and/or low vaccine effectiveness. Additionally, meningococcal disease has declined during the past decade in England and Wales.

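### Impact is a stated objective, but the protocol observes only the three years after launch and plans only descriptive counts, so the plan as written yields no impact estimate

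*Protocol*

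**What the plan says.** Protocol section 8 sets the objective: "to assess the impact on invasive meningococcal disease (all capsular groups) and effectiveness of 4CMenB vaccination against MenB and vaccine-type disease". Section 9.7.1 is firmer: "This study determines the impact on meningococcal disease". The title-page objective and the Abstract (section 4) also name impact, although the Abstract limits it to MenB.

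The observation window is fixed in several places:
- The opening text of section 9: "Observations will start with introduction of the vaccine into routine clinical care in England and last for the 3-year study duration".
- The milestone table in section 6 dates the start of data collection: "With launch in the UK NIP, expected 1 Sep 2015".
- Section 9.2.1 gives both study parts a three-year observation period, and section 9.2.2 takes the cases reported in that timeframe.
- Section 9 also mentions retrospective reporting, but of cases collected during the same three years.

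On method, section 9.7.3 says of the descriptive part: "The method will be purely descriptive and summarise the observed number of" reported cases, stratified by variables of interest. The analytical part is VE by the screening method, or by case-control if coverage data fail. Section 9.9 notes that "meningococcal disease has declined during the past decade in England and Wales", as a feasibility limitation.

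**The concern.** Impact of a vaccination programme is a change in population disease burden relative to what would have occurred without it, so it needs a comparator: earlier years, unaffected age groups, or both. The protocol appears to share this view. Section 7 reads MenC vaccine impact from the fall after 1999 in a 1998-2010 series (Figure 1) and expects 4CMenB impact data in the same context. The planned design leaves out the 'before' part of such a series.

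At stake is what the six-monthly and final reports can say on impact. With no planned comparison, a reader will probably set post-launch counts beside the older figures in the protocol. A background decline would then be credited to the vaccine, and a background rise would hide an effect.

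**Working it through.** **1. What the protocol sizes.** No size or precision is given for impact. The stated 175 cases (section 9.5: coverage 90%, VE 60%, lower limit 40%) reproduces as a VE calculation. The vaccinated proportion of cases is p = 3.6/4.6 = 0.7826 at VE 60% and 5.4/6.4 = 0.84375 at VE 40%. Then n = 1.96² × 0.7826 × 0.2174 / (0.84375 − 0.7826)² = 174.8, i.e. 175. It concerns vaccinated against unvaccinated children, not burden before and after.

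**2. What an impact estimate needs, and what is planned.**

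| Element | In the protocol |
|---|---|
| Pre-introduction years | Not in the window (sections 6, 9, 9.2.1). The 1998-2010 and 2009-2010 figures serve as background and for the projection in Table 3 |
| Incidence rates | Background only (Figure 3). Section 9.7.3 plans counts |
| Contrast with non-eligible ages | None specified, though such cases are collected (sections 9.2.2, 9.2.3) |
| Effect measure | VE only (section 9.7.3) |
| Other capsular groups | In the objective; section 9.7.3 expects too few cases for analysis |

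**3. How far trend could distort an informal comparison.** Table 3's planning reductions reproduce:
- Under 1 year: 210 × 5/12 + 210 × 7/12 × (0.1 + 0.9 × 0.5) = 154.9, a 26.2% reduction.
- Age 1 year: 119 × (0.1 + 0.9 × 0.4) = 54.7, a 54.0% reduction.

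The annual background decline d is not given, so 0% to 10% is assumed. The apparent reduction after k years is 1 − (1 − d)^k × (1 − r), where r is the vaccine reduction. From 2009-2010 to mid-study, k is about 7. From the last year before launch, k is about 2.

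| d per year | Trend alone, k = 7 | <1 year, k = 7 | 1 year, k = 7 | Trend alone, k = 2 | <1 year, k = 2 | 1 year, k = 2 |
|---|---|---|---|---|---|---|
| 0% | 0% | 26.2% | 54.0% | 0% | 26.2% | 54.0% |
| 3% | 19.2% | 40.4% | 62.8% | 5.9% | 30.6% | 56.7% |
| 5% | 30.2% | 48.5% | 67.9% | 9.8% | 33.4% | 58.5% |
| 10% | 52.2% | 64.7% | 78.0% | 19.0% | 40.3% | 62.7% |

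Table 3 also covers England and Wales, whereas the study population is England, so it would not be a like-for-like baseline.

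**4. What a planned contrast does.** If eligible and non-eligible ages share the trend, the ratio of their post/pre ratios is (1 − d)^k (1 − r) / (1 − d)^k = 1 − r, and d cancels.

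**5. Whether counts would support it.** On Table 3's numbers, with one baseline year and Poisson variation only, the post/pre ratio under 1 year is (465/3)/210 = 0.74, with standard error on the log scale √(1/210 + 1/465) = 0.083 and 95% interval 0.63 to 0.87. At age 1 year it is (164/3)/119 = 0.46, interval 0.36 to 0.58. The comparison ages add variance; further baseline years reduce it.

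**The case against.** The best defence is that impact is openly descriptive here. No hypothesis is tested, section 7 gives effectiveness as the purpose, and all sizing concerns VE. Being named first does not make impact primary. An analysis plan not shown here could hold the model, and section 9.7 allows further analyses if they are defined before enrolment. Much of this stands: model form and the number of baseline years are details for an analysis plan. The observation window and the counts-only method, however, are set in the protocol.

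Two stronger readings are tempting, and the document does not support them.

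- A reader might infer that impact cannot be estimated at all, or that post-launch counts carry no information. The descriptive part covers the general population, by age and vaccination status. Non-eligible ages are therefore in the data, and under the anticipated infant schedule eligible cohorts age in over the three years. National surveillance also predates launch. What is missing is a planned comparison.
- A reader might infer a background MenB fall of about 21%, from over 1,000 cases a year to 785, as large as the 26% expected in infants. The first figure is a rounded statement about England citing 2008-2009 data; the second is an England and Wales count for 2009-2010. The contrast also sets an all-age change against the smaller of two age-specific effects, omitting 54% at age 1 year. Section 7 calls the MenB decline slight. The decline in section 9.9 is for meningococcal disease generally, and section 7 attributes the drop in MenC to a vaccine.

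**Conclusion.** The point holds as a mismatch between objective and method. The protocol promises an assessment of impact, and the plan as written produces none. This follows from the text and does not depend on any trend figure.

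The size of the bias in an informal comparison is unknown because the MenB trend is not given. The table above shows only how sensitive such a comparison would be, taking Table 3's reductions as given and the decline rates as assumptions. A slight decline, as section 7 describes it, would point to the lower rows of bias, but no rate can be read from the protocol.

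The VE objective is untouched, since it compares vaccinated with unvaccinated children in the same birth cohorts.

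**What to change.** In sections 9 and 9.7.3, add several pre-introduction epidemiological years from the same national surveillance, restricted to the study's geography and with population denominators. Name the impact measure: the post/pre incidence rate ratio in vaccine-eligible cohorts relative to the same ratio in non-eligible age groups, for MenB and, where counts allow, for other capsular groups. State the assumptions: parallel trends across the age groups, and no indirect effect of vaccination on the comparison ages. The regression model can be left to the analysis plan.

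The cost is a small additional analysis. It should need no new case collection, since the surveillance predates launch, but its result rests on those two assumptions.

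If this is not wanted, remove impact from the title-page objective, the Abstract, section 8 and section 9.7.1, and describe that part as descriptive surveillance.

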9.1 Study Design

The proposed designs of the study are as follows:

- 1. Descriptive study (no hypothesis testing): summary of the epidemiology of meningococcal disease, by vaccination status, age, etc. This description would focus on the epidemiology not only of MenB, but, if possible, also include other capsular groups in order to evaluate both cross protection against meningococci with other capsular groups and any replacement that may occur after introduction of the vaccine.
- 2. Analyses for effectiveness of 4CMenB will be performed prospectively using the screening method (see a brief outline below). If the screening method is inapplicable then a case control method would be used. All these study designs have successfully been used to assess effectiveness of the MenC conjugate vaccine in England [Bose A et al., 2003], [Ramsay ME et al., 2001], [Trotter CL et al., 2004].
- 3. Similarly to other retrospective methods, the screening method is based on a comparison of the proportion vaccinated among the cases and the population. However, it differs from other methods in that control is achieved by external standardisation, using an estimate of vaccine coverage which is derived from sources external to the study [Farrington CP, 1993].

9.2 Setting

9.2.1 Study Period

[figure not shown]
Overall study period

The overall study period will consist of the 3-year study duration, and time needed for analysis of data, production of the final report and writing of publication(s). The latter is estimated to take approximately 6 months. A figure depicting the study timelines is given below (Figure 4).

Observation period

The observation period will be 3 years, during which the descriptive and analytical study will take place.

Study timelines

¹ EMA registration Jan 2013

² UK introduction expected Sep 2015

³ Start of study expected Sep 2015 (with introduction into NIP)

⁴ Total study duration 3 years

9.2.2 Study Subjects

All meningococcal cases reported during the above mentioned timeframe(s) will be included in both parts of the study (descriptive and analytical). Data from the national surveillance on meningococcal disease, as well as vaccination status of the cases, will be collected through PHE in England.

9.2.3 Study Population Selection

The study population for the descriptive part of the study is the general population in England. Individuals will be included in the cohorts targeted for vaccination in England. Exploratory analyses could be envisioned for other regions (Northern Ireland, Wales, Scotland), if data become available.

Inclusion Criteria

Case definitions are given in section 9.4.2. Final criteria for 4CMenB failure will depend on the schedule for use of 4CMenB in the population. The design of the study will also affect inclusion criteria, e.g. for case-control study controls will be included as defined in section 9.5.

Exclusion Criteria

Excluded will be those who have not been offered the vaccine (e.g. immigrants) and individuals who were not vaccinated according to the NIP (partially vaccinated). From previous vaccine studies, we know that the proportion partially vaccinated will be low (PHE personal communication).

9.3 Variables

9.3.1 Exposure of Interest

GSK Vaccines' 4CMenB vaccine is used in this study as part of routine clinical care, e.g. as recommended in the NIP. Information on how the commercial product should be stored and administered is in accordance with applicable national or EU guidelines and is described in the package insert. Co-administration of other vaccines may occur as consistent with clinical practice.

Indication and schedule

The 4CMenB was registered in Europe in January 2013. The indication of the 4CMenB vaccine is for active immunisation against invasive disease caused by MenB strains in individuals from 2 months of age and older (3+1 schedule).

The anticipated schedule for 4CMenB in the UK is:

- 1. Infants standard routine at age 2, 4 with a booster at 12 months (2+1 schedule, 3 doses in total)
- 2. Infants for a NIP with small catch-up campaign, e.g. at age 3 and 4 months with a booster at 12 months (3 doses in total), or at 4 months with a booster at 12 months (2 doses in total)

9.3.2 Outcome(s)

The primary outcome is a capsular group B confirmed case by culture and/or PCR from a normally sterile site (case definition A), regardless of MATS.

The secondary outcome is a confirmed or probable case of capsular group B 4CMenB-vaccine-type where protection would have been expected based on the vaccine antigens (case definition B).

Additional calculations can be envisioned to investigate the dose-response relationships for each antigen in the vaccine (versus having at least one antigen, as described in the secondary objective). Exploratory analyses on the effectiveness of 4CMenB against other meningococcal capsular groups could take place at a later stage.

9.3.3 Other Variables

Vaccination status, age and gender, will be collected for the screening method. Dates of exposure are essential to allow for sensitivity analyses on the index dates.

9.4 Data Sources

Exposure of interest

Data for this study will be collected through the national surveillance system, as well as an additional source(s) to collect data regarding vaccinations. All cases of confirmed MenB disease will routinely be followed up to obtain vaccination history (including batch number) through enhanced surveillance by PHE. Additionally, demographics and medical history will be ascertained.

For the analytical study the screening method will be used. As above, vaccine history of confirmed cases will be collected to assess the proportion of cases that were fully vaccinated (PCV).

The comparator will be national vaccination rates as the proportion population vaccinated (PPV). These data may for instance be taken from the Cover Of Vaccination Evaluated Rapidly (COVER) system which collects data about the coverage of routine infant vaccination from health authorities in England, and/or from a general practice database [Anon, 1999]. COVER data would have some limitations as it only provides coverage at fixed time points (12, 24 months) and we would not know about partial vaccination. Data will therefore be supplemented by disaggregate data obtained from either general practice or child health database to provide estimates of dose specific coverage at specific ages.

Outcomes of interest

The study will be partnered with Public Health England (PHE) and its Meningococcal Reference Unit (MRU) in England, so that national laboratory surveillance data for meningococcal disease can be used [Gray SJ et al., 2006]. PHE's national surveillance system consists of statutory reporting of confirmed invasive meningococcal disease by laboratories. Statutory notification by physicians to local units of PHE ensures rapid follow up of clinically diagnosed cases and helps to ensure complete laboratory investigation. Clinical specimens and isolates of *Neisseria meningitidis* are also referred for capsular group specific PCR and routine serogrouping and subtyping.

In addition, all isolates referred to MRU from individuals eligible for vaccination will have qualitative and quantitative assessment of meningococcal antigens (Meningococcal antigen typing system or MATS) will be evaluated for each case where the organism is identified by culture. For cases with PCR-only confirmation of capsular group B (no

GSK Vaccines S.r.l.		Observational Study Protocol V72_38OB
03 SEP 15 Version 3 Final	Confidential	Page 31 of 61

isolate available from sterile site), but where a capsular group B isolate from a throat swab is available, MATS will be performed on the throat isolate instead.

GSK Vaccines will provide MATS kits to MRU.

If it is decided to pursue a case-control study instead of using the screening method, for instance if uptake information is difficult to obtain, three controls per case will be selected from the same population as where the cases arose from. This can for instance be from the same general practitioner's practice or local health economy, as where the case is registered in order to control for residential area. Three controls per case could be matched by age at the date the case occurred (date of month) and gender.

9.4.1 Operational Exposure Definition

Vaccination status by individual, including the type of vaccine, batch number and date of vaccination, is included in the enhanced surveillance system.

9.4.2 Operational Outcome Definition and Identification Process

A case of *Neisseria meningitidis* is defined by culture of *Neisseria meningitidis* or identification of meningococcal DNA from a normally sterile site. For the purposes of surveillance cases will be further classified as:

A. A case of capsular group B *Neisseria meningitidis* is defined as isolation of capsular group B *Neisseria meningitidis* or positive capsular group B specific PCR from a normally sterile site.

B. Capsular group B-vaccine-type

- I. Confirmed case capsular group B-vaccine-type:
 - a. Isolation with ≥ 1 vaccine antigen above positive bactericidal threshold (PBT) by MATS-ELISA or PorA P1.4 from a normally sterile site (**MATS-positive**), or
 - b. PCR on a normally sterile site + B isolation from throat swab with ≥ 1 vaccine antigen above PBT by MATS-ELISA or PorA P1.4 (MATS-positive), or
 - c. PCR on a normally sterile site + PorA P1.4 identified on genosubtyping
- II. **Probable case capsular group B-vaccine-type:** PCR on a normally sterile site + fHBP sub-variant 1, 4, 37, 232
- III. **Unlikely case capsular group B-**vaccine**-type:** isolation (Ia or Ib) from a normally sterile site with three vaccine antigens below positive

bactericidal threshold (PBT) by MATS-ELISA + PorA P1 \neq 4 (**MATS-negative**)

IV. Indeterminate case – capsular group B-vaccine-type: capsular group B, but not in I, II, III

[figure not shown]
Vaccine (Bexsero) failure against vaccine-type-specific B disease: Reported to authorities

[figure not shown]
- Case as defined for above subgroup I or II *, and
- Confirmation that patient was age appropriately and fully vaccinated as recommended and with a reasonable delay for full effect of immunization, e.g. effectiveness of primary vaccination:
 - a. At least 14 days after the 3rd injection in the routine schedule (standard primary infant and booster), or
 - b. If primary vaccination was not given as part of the standard routine infant schedule, then at least 14 days after the 2nd injection

(* Subgroups III and IV: fully vaccinated reported to authorities, but not defined as vaccine failure)

[figure not shown]
Our analyses will only include individuals in England fully and timely vaccinated according to the routine, standard national immunization schedule as described in section 9.3.1. Exploratory analyses could be envisioned such as for other schedules (e.g. catch-up at 3,4,12 months or 4,12 months), capsular non-B, other regions (Wales, Scotland), if data become available.

Following these definitions, please find a flowchart with the meningococcal case identification process and case definitions below (Figure 5).

Depending on results, fulfilling case definition A or B (or none of these)

**** Only capsular group B (case definitions A or B) or none of these NB: vaccine failure: A or B, and appropriately vaccinated at least 14 days before

9.4.3 **Operational Variable(s) Definition**

See above under 9.3.3 and 9.4.2.

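### Class Ib lets a group B throat isolate decide Confirmed vaccine-type, with no rule for when the sterile-site PorA or fHbp type says otherwise

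*Protocol*

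**What the plan says.** Section 9.4 (Data Sources, outcomes of interest) covers group B cases with PCR confirmation and no sterile-site isolate, "but where a capsular group B isolate from a throat swab is available, MATS will be performed on the throat isolate instead". Section 9.4.2 then classifies the case, and the Abstract repeats the definitions:

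- **Class Ib, Confirmed:** "PCR on a normally sterile site + B isolation from throat swab with" at least one antigen above threshold by MATS-ELISA, or PorA P1.4.
- **Class Ic, Confirmed:** "PCR on a normally sterile site + PorA P1.4 identified on genosubtyping".
- **Class II, Probable:** "PCR on a normally sterile site + fHBP sub-variant 1, 4, 37, 232".
- **Class III, Unlikely:** "isolation (Ia or Ib) from a normally sterile site with three vaccine antigens below positive" threshold, with a PorA other than P1.4.
- **Class IV, Indeterminate:** any other group B case.

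Section 9.3.2 builds the secondary outcome from the first two categories: "The secondary outcome is a confirmed or probable case of capsular group B 4CMenB-vaccine-type where protection would have been expected". The vaccine-failure definition in section 9.4.2 also rests on classes I and II. The primary outcome is any confirmed group B case, whatever its MATS result.

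**The concern.** Class Ib treats the throat organism as if it were the invading one. A child can carry one group B strain and be invaded by another. If the carried strain is MATS-positive and the invading strain is not a vaccine type, the case is still Confirmed. That holds even when the sterile-site PorA or fHbp result shows a different strain, because no listed condition compares the two specimens and no order of precedence is given.

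The means of checking is already in the plan. Classes Ic and II use PorA and fHbp typing alongside sterile-site PCR, and section 9.4 says that clinical specimens, not only isolates, are referred for subtyping. These results can admit a case but are never used to test the throat isolate.

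At stake is the vaccine-type part of the study objective (section 8). The secondary outcome is meant to hold cases in which the vaccine should have worked. A vaccinated child wrongly placed in class Ib lowers the VE estimate and can be counted as a vaccine failure.

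**Working it through.** **Inputs from the protocol.** Coverage 90% and VE 60% (section 9.5); strain coverage 78%, with 73–87% by country (section 7); PCR-only share 50–60% of cases with a confirmed group (section 9.8.1), taken here to apply to group B.

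**Inputs assumed, because the protocol does not give them.** f is the share of group B cases typed on a throat isolate, 5–60%; the upper end is the whole PCR-only share. d is the share of those isolates that are not the invading strain, 10–30%. Carried strains are MATS-positive at the same 78%. VE against non-vaccine-type strains is 0. All other cases are classed correctly. Discordance is unrelated to vaccination.

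**The plan's own figure, for scale.** The proportion of cases vaccinated is PCV = PPV(1−VE)/(1−PPV×VE). At VE 60% this is 0.36/0.46 = 0.7826; at VE 40% it is 0.54/0.64 = 0.8438. A Wald interval on PCV needs n = 1.96² × 0.7826 × 0.2174 / (0.8438 − 0.7826)² ≈ 175 (unrounded PCVs), matching Table 1. The planned precision is thus 20 points from estimate to lower limit. Nothing below changes the 175.

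**Bias.** Among unvaccinated cases:

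- truly vaccine-type and so labelled: 0.78 × (1 − 0.22fd)
- another strain but labelled vaccine-type: 0.22 × fd × 0.78

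The sum is 0.78, so the contaminating share is m = 0.22fd. The estimated relative risk is 0.40(1−m) + m, which gives VE = 0.60(1−m). The loss is 0.60 × 0.22fd = 0.132fd.

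| f | d | VE estimated |
|---|---|---|
| 5% | 10% | 59.9% |
| 20% | 10% | 59.7% |
| 20% | 30% | 59.2% |
| 40% | 30% | 58.4% |
| 60% | 10% | 59.2% |
| 60% | 30% | 57.6% |

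**Sensitivity of the range.**

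- Strain coverage 73% or 87% at f = 40%, d = 30% gives 58.1% or 59.1%.
- If no other PCR-only case reaches class I or II, throat-typed cases are f/(f + 0.40) of those labelled. At f = 20%, d = 30%, m = 0.22 × 0.30 × 0.333 = 2.2% and the loss is 1.3 points instead of 0.8. The ceiling at f = 60% is unchanged.
- If 60% is the VE against all group B disease, vaccine-type VE is 60/78 ≈ 77%. At f = 60%, d = 30%, m = 3.96% and the estimate is 0.77 × 0.9604 = 74.0%, a loss of about 3 points.

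**Related to vaccination.** At f = 20%, d = 10% (fd = 2%), suppose vaccination lowers carriage of MATS-positive strains by 30% or 50%. VE is then 59.8% or 59.9%. If it abolished such carriage, the relative risk would be 0.40 × 0.98 = 0.392 and VE 60.8%. The direction is therefore fixed only when discordance is unrelated to vaccination.

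**The reverse error.** If a MATS-negative carried strain removes true vaccine-type cases at the same rate in vaccinated and unvaccinated children, the factor cancels in the screening formula. Cases are lost, but this alone does not bias the estimate.

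**The case against.** The strongest reply is that the effect is small and the rule is not unguarded. Both specimens must be group B: section 9.4 limits throat MATS to cases with PCR-confirmed group B, and Ib sits under the group B heading. A reader might infer from class Ib alone that any sterile-site PCR signal suffices; the documents do not support that. What is missing is agreement below the level of capsular group.

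A false Confirmed case also needs several things at once: PCR only, a throat isolate, a discordant strain, a non-vaccine-type invader and a MATS-positive carried strain. A reader might infer from the 50–60% PCR-only share that contamination of 5% or 10% is likely, which would take a vaccine-type VE of 77% to about 73% or 69%. With m = 0.22fd, those levels need fd of about 23% or 45%. Even at f = 60%, d would have to be about 38% or 76%. Nothing in the documents supports that.

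A reader might also infer that a throat isolate can make a true vaccine-type case Unlikely and so bias VE. Class III contradicts itself here: it cites Ib, which is throat-based, yet requires a sterile-site isolate. On either reading the main cost is precision, and fully vaccinated class III and IV cases are still reported to the authorities.

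Two further points stand. Figure 5, the case-identification flowchart, is not shown and could hold a precedence step. The protocol also does not say that sterile-site typing succeeds for every PCR specimen, so a rule that removed all untyped Ib cases would cost precision that section 9.9 already flags as a feasibility risk.

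None of this answers the core point. As written, a case whose own sterile-site type contradicts the throat isolate is still Confirmed.

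**Conclusion.** The point holds in limited form. In the visible text, class Ib requires agreement on capsular group only and says nothing about conflicting PorA or fHbp results. It can therefore put non-vaccine-type cases into the secondary outcome and the failure definition. With strain coverage 78%, true VE 60% and discordance unrelated to vaccination, the downward bias is about 0.1 to 2.4 points over f = 5–60% and d = 10–30%. Both ranges are assumptions. This is small beside a planned lower limit 20 points below the estimate, and the primary outcome is untouched. The case for acting is that the definition is wrong for an identifiable set of cases and is cheap to correct.

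**What to change.** 1. Add to class Ib: where a sterile-site PorA genosubtype or fHbp sub-variant is available and disagrees with the throat isolate, the throat isolate is ignored and the case is classed on the sterile-site result (Ic, II or IV).
2. Keep Ib cases without sterile-site typing in the main secondary analysis, and report a sensitivity analysis of secondary VE that excludes them.
3. Reconcile class III: either remove the reference to Ib, or state that a throat isolate may be used and apply the same precedence rule to it.
4. Make the same changes in the Abstract and check that Figure 5 agrees.

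The cost is definition wording, one sensitivity analysis, and perhaps a few cases moved from class I to II or IV. The typing it draws on is already part of the plan, and no sample-size figure changes.
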